10.2 Continuing Pembrolizumab

In the event of radiological progression, pembrolizumab may be continued if there is evidence of clinical benefit in the opinion of the investigator if there are no signs or

symptoms indicating unequivocal disease progression, no decline in ECOG performance status attributed to disease progression and no growth of the tumour in critical sites. If radiological progression is still documented pembrolizumab may still be continued until there is unequivocal symptomatic deterioration attributed to disease progression that requires initiation of new systemic therapy. Radiotherapy to progressing or symptomatic sites as per standard clinical practice is allowed.

11. Labeling, Packaging, Storage and Return of Clinical Supplies

11.1 Investigational Product

The investigator shall take responsibility for and shall take all steps to maintain appropriate records and ensure appropriate supply, storage, handling, distribution and usage of investigational product in accordance with the protocol and any applicable laws and regulations.

Clinical Supplies will be provided by Merck as summarized in Table 8.

Table 8: Product Descriptions

Product Name & Potency	Dosage Form
Pembrolizumab 50 mg	Lyophilized Powder for Injection
Pembrolizumab 100 mg/ 4mL	Solution for Injection

11.2 Packaging and Labelling Information

Clinical supplies will be affixed with a clinical label in accordance with regulatory requirements.

11.3 Clinical Supplies Disclosure

This trial is open-label; therefore, the patient, the trial site personnel, the Sponsor and/or designee are not blinded to treatment. Drug identity (name, strength) is included in the label text; random code/disclosure envelopes or lists are not provided.

11.4 Storage and Handling Requirements

Clinical supplies must be stored in a secure, limited-access location under the storage conditions specified on the label.

Receipt and dispensing of trial medication must be recorded by an authorized person at the trial site.

Clinical supplies may not be used for any purpose other than that stated in the protocol.

11.5 Returns and Reconciliation

The investigator is responsible for keeping accurate records of the clinical supplies received from Merck or designee, the amount dispensed to and returned by the patients and the amount remaining at the conclusion of the trial.

Upon completion or termination of the study, all unused and/or partially used investigational product will be destroyed at the site per institutional policy. It is the Investigator's responsibility to arrange for disposal of all empty containers, provided that procedures for proper disposal have been established according to applicable federal, state, local and institutional guidelines and procedures, and provided that appropriate records of disposal are kept.

12. Adverse Events

12.1 Adverse Event Definition

An Adverse Event (AE) is any untoward medical occurrence in a patient or clinical investigation patient administered a pharmaceutical product (or any other protocol specified intervention including radiation therapy, surgery or use of a device) and which does not necessarily have to have a causal relationship with this treatment.

An AE can therefore be any unfavourable and unintended sign, symptom or disease temporally associated with the use of a medicinal product, whether or not related to the medicinal product (or associated with the use of any other protocol specified intervention including radiation therapy, surgery or use of a device).

AEs include: 'Adverse Drug Reactions', i.e. a reaction, in contrast to an event, is characterised by the fact that a causal relationship between the drug and the occurrence is suspected.

For unapproved medicines: any noxious and unintended response to a medicinal product, related to any dose. The phrase "response to an unapproved medicinal product" means that a causal relationship between the product and an adverse event is at least a reasonable possibility, i.e. the relationship cannot be ruled out. ('Unapproved medicinal product' here includes approved products used at levels or in ways that are unapproved).

Regarding marketed medical products: a noxious and unintended response to a drug that occurs at doses normally used in humans for prophylaxis, diagnosis or therapy of diseases or for modification of physiological function.

12.2 Unexpected Adverse Event Definition

An unexpected adverse event (UAE) is an AE for which the nature or severity of the event is not consistent with the information in the relevant source documents e.g. the IB, published information, product information (or with the applicable side effect risk profile for radiation therapy, surgery or use of a device).

UAEs also include unexpected adverse drug reactions (UADR) - The nature and severity of the ADR is not consistent with the information in the Investigators Brochure for an unapproved investigational product, or the product information/package insert/summary of product characteristics for an approved product.

12.3 Serious Adverse Event Definition

Adverse events and adverse drug reactions are considered 'serious' if they threaten life or function.

Due to the significant information they provide, serious adverse events (SAE) (including Serious Adverse Drug Reactions) require expedited reporting. SAEs are defined as any adverse event or adverse drug reaction which:

- Results in death (i.e. fatal/grade 5 CTCAE)
- Is life-threatening (i.e. grade 4 CTCAE)
- Requires inpatient hospitalisation or prolongation of existing hospitalisation
- Results in persistent or significant disability/incapacity; or
- Is a congenital anomaly/birth defect
- Is a new cancer (that is not a condition of the study)
- Is associated with an overdose
- Other significant medical event*

*Medical and scientific judgment should be exercised in deciding whether expedited reporting is also appropriate in other situations, such as important medical events that may not be immediately life threatening or result in death or hospitalization but may jeopardize the patient or may require intervention to prevent one of the other outcomes listed in the definition above. These should usually be considered serious.

The following are NOT considered SAEs:

- Hospitalizations not intended to treat an acute illness or adverse event (e.g., social reasons such as pending placement in long-term care facility).
- Surgery or procedure planned before entry into the study. Note: Hospitalizations that were planned before the signing of the PICF, and where the underlying condition for which the hospitalization was planned has not worsened, will not be considered serious adverse events. Any adverse event that results in a prolongation of the originally planned hospitalization is to be reported as a new serious adverse event.
- Disease progression should NOT be reported as an adverse event or serious adverse event term; instead, signs and symptoms of clinical sequelae resulting from disease progression/lack of drug efficacy will be reported if they fulfill the serious adverse event definition.
- A standard procedure for protocol therapy administration will not be reported as a serious adverse event. Hospitalization or prolonged hospitalization for a

complication of therapy administration will be reported as a serious adverse event.

- The administration of blood or platelet transfusion. Hospitalization or prolonged hospitalization for a complication of such transfusion remains a reportable serious adverse event.
- A procedure for protocol/disease-related investigations (e.g., surgery, scans, endoscopy, sampling for laboratory tests, bone marrow sampling, pharmacokinetic or biomarker blood sampling). Hospitalization or prolonged hospitalization for a complication of such procedures remains a reportable serious adverse event.
- Prolonged hospitalization for technical, practical, or social reasons in the absence of an adverse event.

12.4 Attribution

Attribution of cause requires at least a reasonable possibility of a causal relationship between the event and the use of the investigational drug or any other protocol-specified intervention.

All protocol-specified interventions (including pharmaceutical products, radiation therapy, surgery or use of a device) administered prior to the date of the event must be attributed a degree of causality from one of the following codes:

RELATIONSHIP	ATTRIBUTION	DESCRIPTION
Unrelated	Unrelated	The AE is clearly NOT related to the intervention
	Unlikely	The AE is doubtfully related to the intervention
Related	Possible	The AE may be related to the intervention
	Probable	The AE is likely related to the intervention
	Definite	The AE is clearly related to the intervention

12.5 Severity Criteria

An assessment of severity grade will be made using the NCI-CTCAE (version 4.03). Where parameters are not addressed within the criteria, severity of AEs should be graded as:

Mild	Aware of sign or symptom, but easily tolerated
Moderate	Discomfort enough to cause interference with usual activities
Severe	Incapacitating with inability to work or perform usual activities
Life-threatening	Patient is at immediate risk of death
Fatal	Death

12.6 Adverse Events Reporting

All adverse events, which occur whilst the patient is enrolled on the trial, must be reported in the patients' medical records and recorded on the relevant CRF.

12.7 Evaluating Adverse Events

An investigator who is a qualified physician will evaluate all adverse events according to the NCI Common Terminology for Adverse Events (CTCAE), version 4.03. All adverse events regardless of CTCAE grade must also be evaluated for seriousness. Laboratory values need reporting as AEs only if abnormal and deemed clinically significant by the investigator.

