Trial Phase:	Screening Phase	Treatment Phase			Follow-up Phase		Progression
Trial phase and windows	Screening -28 to -1	Day 1 Cycle 1 3 days \pm 2 days prior to the first dose of pembrolizumab	SABR 7 days \pm 2 days from cycle 1 day 1	Day 1 Cycle 2-34 3 days \pm 2 days prior to each dose of pembrolizumab	Safety Follow-up 30 days \pm 3 days from date of last dose of pembrolizumab	Follow-up 3 months \pm 7 days from the last cycle of pembrolizumab	Upon first progression ¹
Biochemistry ⁶	X	X		X		indicated	
Thyroid Function tests ⁷	X	X		X			
Coagulation profile ⁸	X	X		X			
Virology ⁹	X						
Tumour Evaluation							
CT scan (Brain, Chest, Abdo, Pelvis) reported with RECIST 1.1 or MRI ¹⁰	X			X		X	
Whole body bone scan ¹⁰ (if clinically indicated)	X			X		X	
Response assessment ¹⁰				X		X	
FDG-PET ¹⁰	X			X ¹¹			
Translational studies							
Fresh tumour biopsy sample ¹²	X					X	X
Archival tumour biopsy sample ¹³	X						
Blood Collection ¹⁴ (serum and ctDNA)		X	X	X		X	X

Table 1 and 2 Footnotes

1. Beyond first progression, every effort should be made to record results of subsequent tumour assessments. In addition, details of any new anti-cancer treatment commenced is to be collected.
2. Vital signs include blood pressure, heart rate, respiratory rate and temperature. Body measurements including height and weight (height only required at screening).
3. Urine or serum pregnancy test for patient of childbearing potential should be performed within 7 days randomisation and also 72 hours before first dose of pembrolizumab. If the urine test is positive or cannot be confirmed as negative, a serum pregnancy test will be required.
4. Baseline abnormalities must be recorded from signature of informed consent to prior to start of treatment. Adverse events (using CTCAE v4.03) are then required to be reported on completion of SABR, day 1 of every pembrolizumab cycle and at every follow-up visit. If at any time, a patient commences a new anti-cancer therapy, recording of adverse events is no longer required.

Laboratory Procedures/Assessments – All diagnostic laboratory tests should be performed within 10 days of randomisation (to determine eligibility), and also on day 1 ± 3 days of every cycle of pembrolizumab (unless otherwise specified)

5. Haematology: Haematocrit, haemoglobin, platelet count, white blood cell count (total and differential), red blood cell count, absolute neutrophil count and absolute lymphocyte count.

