6. Biochemistry: calcium chloride, glucose, phosphorus, potassium, sodium, magnesium, total protein, Liver Function Tests: Albumin, Alkaline Phosphatase (ALP), Alanine Aminotransferase (ALT), Aspartate Aminotransferase (AST), Lactate Dehydrogenase (LDH), Gamma-Glutamyl Transferase (GGT), total bilirubin (+direct bilirubin if total bilirubin is elevated above the ULN), Kidney Function Tests: Urea, creatinine.
7. Thyroid Function tests: T3, T4 and TSH. To be performed at during screening, day 1 cycle and every 6 weeks thereafter.
8. Coagulation Profile: PT (INR), aPTT.
9. Virology: HIV, Hepatitis B and C tests only required for those patients at risk of prior or current active infection as determined by the investigator. To be performed within 21 days of randomisation.

Tumour evaluation

10. Radiological tumour assessments will be performed by CT scan (or MRI as required if tumour is in extremity) at screening (within 6 weeks of randomisation), prior to cycle 3, 5, 7 and every 3 cycles thereafter in the treatment phase. Then 3 monthly in the follow-up phase until the last patient recruited completes 24 months of follow-up, unless evidence of progression earlier. Whole body bone scan (WBBS) will be performed if clinically indicated at the same time points. Formal response assessment (using RECIST 1.1, irRECIST, Peter Mac Metabolic Response Criteria and PERCIST 1.0.) at each scheduled scan time point. Response should be confirmed with repeat imaging 4 to 8 weeks later by the same imaging modality. CT of brain only required at screening.
11. FDG PET at baseline and prior to cycle 5 of pembrolizumab. (note: a contemporaneous CT brain/chest/abdo pelvis performed at the same time will fulfill the CT requirement 3 month follow-up)

Biological Evaluations

12. A fresh biopsy of the primary or metastatic lesion will be performed at screening (within 12 weeks of randomisation). and 3 months post completion of SABR. This will ideally be the same site as biopsied before at screening. In event of disease progression, a sample from progressing metastatic site(s), if feasible, is requested. Refer to the SABRseq laboratory manual for further details on handling and shipping of tumour samples.

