5.3 Endpoints

Primary Endpoint

- Toxicities associated with SABR in combination to pembrolizumab are defined as adverse events (AE's) considered possibly, probably or definitely related to the treatment. Safety (acute and long term) will be assessed using CTCAE version 4.03.

Secondary Endpoints:

- Response will be assessed by 4 different methods (RECIST 1.1, irRECIST, Peter Mac Metabolic Response Criteria and PERCIST 1.0) and will be assessed a) only considering irradiated lesions; b) only considering non-irradiated lesions and; c) considering all lesions (overall response rate)
- Overall survival will be measured from the date of randomisation to the date of death from any cause.
- Progression free survival will be measured from the date of randomisation to the date of first progression at any site or date of death due to any cause.
- Event history is defined as the time from the date of randomisation to the date of each event of interest (progression at an irradiated lesion, progression at a non-irradiated lesion, appearance of a new lesion, ceasing treatment and death). Patients alive will be censored at the date of last follow-up.

Exploratory Endpoints

A number of translational endpoints will be evaluated including:

- PD-L1 expression in tumour tissue using immunohistochemistry with the 22C3 antibody using the DAKO Autolink 48 system.

- Tumour infiltrating lymphocytes (TILs).
- Changes in host anti-tumour immunity to look for evidence of immune activation and relief of immunosuppression in tumour tissue and peripheral blood from the patient over time and at time of progression (if this occurs).
 - Blood samples will be collected at multiple time points before, during and after trial related therapies. These will be analysed for biomarkers including, but not limited to, the following (this is a non-exhaustive list):
 - Absolute lymphocyte counts using a blood analyser.
 - The presence of CD8+ T cells by flow cytometric analysis.
 - Change in frequency of tumour reactive T cells. These may include markers for HLA-DR, CD4+, CD8+ T cells, PD-1, TIM-3 signifying antigen presentation and experience.
 - Immune cytokines

6. Trial Design

This is a prospective, open label, two arm randomised clinical trial with 1:1 allocation ratio evaluating the safety, efficacy and immunological effects of two different sequences of pembrolizumab in combination with SABR treatment in NSCLC – pembrolizumab given either before or after SABR.

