7.5 Blinding and Procedures for Unblinding

This is an open-label trial; therefore, the Sponsor, investigator and patient will know the treatment administered

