14.5 Safety Analysis

Safety will be assessed using CTCAE v4.03 and the maximum toxicity grade per patient of each adverse event will be derived and presented in table format according to arm and overall. The number of patients who suffer from grade 3 or higher toxicities (for each toxicity type and overall) will be provided considering all patients who have received at least one dose of pembrolizumab and completed at least one SABR treatment. The safety analysis will be conducted twice: once for all AE's, regardless of relatedness to treatment and once considering only AE's related to the treatment (i.e. classified as possibly, probably or definitely related).

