14.9 Sample Size Calculation

This is a Phase Ib study with a sample size of 32 patients (16 in each arm). This study will assess the common toxicities associated with the combination of SABR and pembrolizumab. The sample size was determined such that, within each arm, the probability of observing toxicity in at least one patient was 80% for toxicities with true incidence rates of at least 10%. Table 9 illustrates different scenarios for true toxicity rates ranging from 5% to 30% with the respective probability of at least one patient presenting with the toxicity within the arm and overall.

Table 9: Probability of at least one patient presenting with a toxicity for different true toxicity rates

True toxicity rate	Within each arm (n=16)	Overall (n=32)
5%	0.560	0.806
10%	0.815	0.966
15%	0.926	0.994
20%	0.972	0.999

The table below shows the expected confidence interval for different response rate scenarios within each arm.

Table 10: Response rate and confidence intervals for different number of responses with n=16

Number of responses	Response rate (95% confidence interval)
6	37.5 (15 – 65)
8	50 (25 – 75)
10	62.5 (35 – 85)
12	75 (48 – 93)

Recruitment will occur over a two-year period. The principal analyses will be 24 months after the last patient has commenced treatment. An interim analysis assessing patterns of failure

and response to therapy based on post-therapy PET response will be performed once all recruited patients have completed 5 cycles of pembrolizumab therapy.

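### Laboratory abnormalities reach the safety tables only if the investigator judges them clinically significant, and no summary of the measured values is planned, so low-grade laboratory toxicities may be under-counted

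*Combined protocol and SAP*

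**What the plan says.** - **Endpoint (5.3).** Toxicities of the combination "are defined as adverse events (AE's) considered possibly, probably or definitely related to the treatment", graded by CTCAE v4.03. The primary objective (5.2) concerns common toxicities.
- **Testing (footnotes to Tables 1 and 2).** Laboratory tests are done to establish eligibility, "and also on day 1 ± 3 days of every cycle of pembrolizumab", unless otherwise specified. This covers haematology, biochemistry (including liver and kidney tests) and coagulation. Thyroid function is less frequent: "To be performed at during screening, day 1 cycle and every 6 weeks thereafter" (footnote 7).
- **From laboratory value to AE (12.7).** "Laboratory values need reporting as AEs only if abnormal and deemed clinically significant by the investigator".
- **Analysis (14.5).** The plan is that "the maximum toxicity grade per patient of each adverse event will be derived and presented in table format according to arm and overall". Counts of grade 3 or higher toxicities are added. The analysis is run once for all AEs and once for related AEs.
- **Numeric exception (12.9).** A combined pattern of raised AST or ALT, raised bilirubin and an ALP below twice the upper limit of normal must go on the AE form, whether or not it is related to treatment.
- **Sample size (14.9).** The design target reads: "within each arm, the probability of observing toxicity in at least one patient was 80% for toxicities with true incidence rates of at least 10" per cent.

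**The concern.** The trial collects a dense, objective series of laboratory results, but the plan makes no direct use of it in the safety analysis. Each value must first pass a judgement for which the protocol gives no criterion. Running 14.5 twice does not help, because both runs start from AEs that have already passed that judgement. Nothing in section 14 summarises laboratory values, shifts from baseline, or grades derived from results.

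The judgement is least clear-cut for patients who start with an abnormal value, and Table 3 admits some: AST and ALT may be up to 2.5 times the upper limit of normal, or 5 times with liver metastases. What is at stake is the completeness of the toxicity description, which is the trial's main product. It also bears on how Table 9 is read for toxicities that show only in the laboratory.

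**Working it through.** **Step 1. Follow one laboratory value through the plan.** Take a scheduled result that meets a CTCAE grade and causes no symptoms.

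1. It is measured under the schedule of events.
2. Under 12.7 it need not be reported as an AE unless the investigator deems it clinically significant.
3. If it is not reported, it is outside both runs of 14.5.
4. The rule in 12.9 rescues it only if it is part of the combined liver pattern.
5. Table 7 links actions to grades of liver, renal and thyroid events, but no section says that reaching a grade makes a value reportable. Blood counts have no specific row in that table.
6. The early termination rule in 14.10 concerns pneumonitis and colitis only.

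Such a value can therefore be absent from every planned table.

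**Step 2. Reproduce Table 9.** Inputs from 14.9: n=16 per arm, n=32 overall, true rate p. Formula: P(at least one) = 1 − (1 − p)^n.

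- n=16, p = 5%, 10%, 15%, 20%: 0.560, 0.815, 0.926, 0.972.
- n=32, same rates: 0.806, 0.966, 0.994, 0.999.

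All eight cells agree with the protocol. The formula treats every patient who has the toxicity as a patient in whom it is seen.

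**Step 3. Slack in the 80% target.** The smallest rate giving 80% with n=16 is 1 − 0.2^(1/16) = 0.0957. At a true rate of 10%, at least 0.0957/0.10 = 95.7% of affected patients must be recorded, so the target is missed once more than about 4.3% are not. This partly reflects a sample size set at the minimum: n=15 gives 1 − 0.9^15 = 0.794.

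**Step 4. Illustration.** Assumption: a fraction f of affected patients has the abnormality judged not significant and left unrecorded, independently between patients. The documents give no value for f. The recorded rate is 0.10 × (1 − f).

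| f (assumed) | Recorded rate | One arm, n=16 | Overall, n=32 |
|---|---|---|---|
| 0 | 0.10 | 0.815 | 0.966 |
| 20% | 0.08 | 1 − 0.92^16 = 0.737 | 1 − 0.92^32 = 0.931 |
| 30% | 0.07 | 1 − 0.93^16 = 0.687 | 1 − 0.93^32 = 0.902 |
| 50% | 0.05 | 1 − 0.95^16 = 0.560 | 1 − 0.95^32 = 0.806 |

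At f=50% the result is simply Table 9's own 5% row. Overall detection stays above 80% throughout this range; the shortfall is within the arm.

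**The case against.** **The endpoint is defined by judgement.** Section 5.3 counts AEs that the investigator attributes to treatment, and 12.7 says when a laboratory value becomes an AE. On that reading, a value judged unimportant lies outside the endpoint and is not missing from it, and Table 9 can be read as referring to recorded AEs. This stands to the extent that the endpoint need not change. Derived grades carry no attribution and could not enter a related-AE endpoint in any case. It does not answer the narrower point that a description of common toxicities leaves out objective results the trial already has.

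**The loss is mostly low grade.** Table 7 attaches an action or a treatment to most liver, renal and thyroid events from grade 2 upward, and a value that prompts one is unlikely to be called insignificant. The liver pattern in 12.9 is captured by number. This also stands. The grade 3 or higher counts should be little affected, although 12.7 sets no grade at which reporting is automatic.

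**Stronger readings that the documents do not support.**

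- A reader might infer that laboratory toxicities are certainly under-reported. The documents show that they can be, but give no figure for how often.
- A reader might infer bias between the arms, because 7.5 says: "This is an open-label trial; therefore, the Sponsor, investigator and patient will know the treatment administered". Both arms receive the same two treatments in a different order, with the same per-cycle laboratory schedule. No direction of bias follows, and 14.5 specifies no between-arm test of toxicity.
- A reader might apply f to the 6.9% hypothyroidism rate in 4.12. That figure is already a rate of reported treatment-related AEs, so reducing it again would apply the filter twice.

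**Conclusion.** The point holds as a possible under-count. It rests on the text alone: an undefined judgement in 12.7, an AE-only analysis in 14.5, and no summary of laboratory values as a fallback, apart from the numeric liver rule in 12.9. The abnormalities most exposed are low-grade and asymptomatic.

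The size is unknown. The fall from 0.815 to between 0.737 and 0.560 per arm is an illustration for assumed f of 20% to 50% at a true rate of 10%. It does not estimate what will happen. It does not invalidate the related-AE endpoint or call for a larger sample. This is a cheap improvement to the completeness of the safety report.

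**What to change.** Leave 12.7 and the related-AE endpoint unchanged. Add to 14.5 a supplementary laboratory table, by arm and overall:

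- For the scheduled haematology, liver, renal and coagulation parameters that CTCAE v4.03 grades by value, derive the grade from the measured value and the local normal range. Do this regardless of whether the result was reported as an AE.
- Show the worst post-baseline grade and the shift from the baseline grade.
- For thyroid tests, show shifts relative to the normal range.
- State the baseline. The screening value suits both arms, because in Arm 1 the cycle 1 tests come after SABR (8.2.2) and 8.2.1 lists no safety laboratory tests before it.
- Place the table beside the AE tables, with a note that it carries no relatedness attribution and supplements them.

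**Cost.** A paragraph of analysis-plan wording, entry of existing local results and normal ranges, and some programming. No new tests, visits or patients are needed. The downside is that more low-grade abnormalities will be shown, so the safety profile will look slightly less favourable.
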